Study Title: Comparison of Breath-Enhanced and T-Piece Nebulizers in Children with Acute Asthma

NCT 02566902

Document type: IRB approved study protocol

Document date/most recent update: 30 July 2017

Initial IRB approval date: August 28, 2015

IRB Continuing review approval dates: August 16, 2016, August 14, 2017

**Research Proposal for Review
Seton Institutional Review Board**

I. Title

Comparison of Breath-Enhanced and T-Piece Nebulizers in Children with Acute Asthma

II. Investigators (co-investigators), Study Team Members, and Institutional Affiliations

Principal Investigator:

[name]
The University of Texas at Austin, Dell Medical School
Dell Children's Medical Center of Central Texas
Austin, TX

Co-Investigators:

[name]
The University of Texas at Austin, Dell Medical School
Dell Children's Medical Center of Central Texas
Austin, TX

III. Source of Funding

This study has received funding from the 2014 Scientific, Education and Research Foundation of UTSW Austin Research/Fellow Grant (SERF-RG) in the amount of \$4997 to cover equipment and gift cards for patient enrollment incentive.

The Dell Children's Medical Center Pediatric Emergency Medicine Fellowship will fund any further expenses incurred.

IV. Hypothesis, Research Questions, or Goals of the Project

The objective of this study is to evaluate the efficacy of two different nebulizers. We hypothesize that albuterol delivered with a breath-enhanced nebulizer will lead to statistically greater improvement in FEV₁ when compared to an equivalent dose delivered via a standard t-piece nebulizer. The primary aim will be to study changes in forced expiratory volume in one second (FEV₁) in patients presenting to an urban pediatric emergency department with a moderate to severe acute asthma exacerbation when utilizing these two nebulizers. Secondary aims will include evaluation of hospital admission rates, emergency department (ED) length of stay (LOS), changes in asthma severity scores, vital sign changes, medication side effects, and total quantity of albuterol given in the ED. A distal aim of the study will be to perform a cost analysis; though we will likely need further clinical trials utilizing multiple dose administration in order to accurately analyze cost.

V. Background and Significance

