Subjects will be identified in triage and will be screened and enrolled by a member of the study team (P1). A research nurse will be available for 6-8 hours per day to serve as the primary enrolling personnel during these hours. Additionally, each of the pediatric emergency medicine fellows and several pediatric emergency medicine attending physicians will be trained and certified for enrollment, and will enroll subjects during evenings, nights, and weekends. We anticipate having study personnel available at a minimum of 18 hours per day for enrollment. The P1 personnel will assess the potential subject and screen potential subjects for inclusion and exclusion criteria as detailed above. As a part of screening, the P1 personnel will perform baseline spirometry measurements prior to consent. Spirometry is a minimal risk procedure that is performed as standard of care in many emergency departments nationwide (either as spirometry, or PEF measurements). Performing spirometry prior to consent will expedite screening, and for children who have FEV₁ greater than 70% predicted or those unable to perform acceptable spirometry, this will allow them to be excluded and their asthma treated more promptly. This will avoid excluded children having to undergo consent prior to being excluded and receiving treatment for their acute asthma. Consent will be obtained from the parent or guardian of all patients, and assent obtained from patients who are at least 7 years of age. If required prior to study enrollment, supplemental oxygen may be administered to maintain oxygen saturation $>$ 90% if there is evidence of hypoxemia on continuous pulse-oximetry. If there is a delay of greater than 15 minutes due to the consent process, a unit dose (2.5mg) of albuterol may be given with a standard t-piece nebulizer up to 3 times as needed. Patients requiring this unit dose of albuterol will still be eligible for enrollment so long as they meet enrollment criteria following this therapy. Following consent, the P1 personnel will record an initial set of vital signs (temperature, heart rate, respiratory rate, blood pressure, and peripheral pulse oximetry), and record baseline asthma scores using multiple previously validated asthma severity scores (PAS and PASS).^{24,25} At this point, study patients will be randomized to receive treatment with either the experimental (breath-enhanced) or control (t-piece) nebulizer. Randomization will be performed with a computerized randomization process. Pre-assigned opaque envelopes will be used in order to conceal randomized assignments, preventing any knowledge of patient assignment to the enrolling personnel. A second

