
member of the study team (P2) will open the subject's randomized folder that will dictate the appropriate therapy arm. P2 will administer a single 5mg dose of albuterol via the appropriate nebulizer as determined by randomization. P1 will be blinded to the treatment arm, whereas P2 will not be blinded. Following 15 minutes of therapy - sufficient time for both treatment arms to be complete - P1 will perform a post-treatment assessment of the subject including a repeat set of vital signs, pulse-oximetry, asthma scoring, and spirometry measurements.

Patients randomized to the "control" arm will receive therapy with our standard ED nebulizer, the Hudson RCI® Micro Mist® nebulizer (Teleflex Medical®, Research Triangle Park, NJ). The treatment will be preferentially administered with a mouthpiece. Patients unable or unwilling to use a mouthpiece (as determined by the P2) will receive therapy with a simple mask (Hudson RCI®, Teleflex Medical®, Research Triangle Park, NJ).

Patients randomized to the "experimental" arm will receive therapy with a NebuTech® HDN®, Breath-Enhanced High Density Jet Nebulizer (Salter Labs®, Arvin, CA). Treatments will be preferentially administered with a mouthpiece. Patients unable or unwilling to use a mouthpiece (as determined by the P2) will receive therapy with a mask. The NebuTech® HDN® allows for a proprietary vented mask, which still utilizes the breath-enhanced features of the system (I-Guard™ Valved Aerosol Delivery System, Salter Labs®, Arvin, CA).

Spirometry measurements will be taken using a handheld spirometer which has been validated in healthy controls (NDD EasyOne®).²⁶ In keeping with the most recent American Thoracic Society guidelines, participants will be asked to perform a minimum of 3 and maximum of 8 forced expiratory maneuvers in order to obtain 3 adequate samples as determined by the device.²⁷ Based on prior data, more than 8 attempts at spirometry may result in patient fatigue which will artificially decrease the patient's performance on lung function testing²⁷. The highest recorded FEV₁ will be used for analysis. Flow-volume loops will be evaluated by a pulmonologist in order to assess adequacy of spirometry measurements for all patients, and those with inadequate loops will be excluded from FEV₁ analysis. The pulmonologist involved will be blinded to therapy arm.

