A member of the research team will collect baseline data from the subject's guardian. Data will be recorded on a standardized form and will include subject demographics (including age, ethnicity, primary care provider), baseline home therapies, and assessment of baseline asthma severity, nature and duration of current symptoms, and treatments prior to ED arrival. Following the post-treatment assessment, the P1 (blinded) study personnel will be asked to predict which nebulizer was utilized in the study, in order to evaluate adequacy of blinding.

Following completion of the experimental stage as detailed above, patients will be released to receive standard of care therapy as determined by the assigned attending ED physician. We anticipate that the majority of patients will receive care according to the DCMC ED asthma pathway, including administration of inhaled ipratropium bromide and an oral systemic glucocorticoid. However, some patients may be treated off of the ED pathway, and variability in subsequent therapy is possible. Data will be recorded on a standardized form

regarding subsequent therapy through the remainder of the patients' ED course. Patients who are admitted to the hospital will be treated according to the standard of care as determined by the inpatient attending physician. Following disposition from the ED, no further data will be obtained from patients.

Sample Size

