Treatment groups will be analyzed on an intention-to-treat basis. The primary outcome for this study is change in FEV₁ from initial presentation to reassessment. By evaluating data from previously performed studies,^{16,18} we have conducted a sample size calculation using an estimated baseline initial FEV₁ of 55% predicted, and an estimated 10% FEV₁ improvement with standard of care. The calculations were performed using STATA 13 statistical software (StataCorp, LP, College Station, TX). In order to detect an improvement differential of 5% (absolute) between treatment arms, with a power of 0.80 and alpha of 0.05, we will need 64 patients enrolled in each arm. It has been shown previously that as few as 35%-65% of patients with severe asthma exacerbations are able to successfully perform peak expiratory flow or spirometry.^{22,28} However other studies have not had significant difficulty with pediatric subjects performing spirometry.¹⁵ Several of these studies evaluated patients as young as 5 years old. Due to the inconsistency of data, and the fact that we will be enrolling patients 6 years and older, we estimate that with sufficient coaching, approximately 60% of patients in this study will be able to successfully complete interpretable spirometry. Based on this, we will need to enroll 213 patients in order to obtain interpretable data on 128 patients. We will perform ongoing flow-volume loop analysis of obtained data in order to adjust our total enrollment goal based on the percentage of subjects with interpretable data sets.

Statistical Analysis

The primary outcome of change in FEV₁ will be compared between the two groups using a two-tailed t-test, or non-parametric equivalent if the data is non-normally distributed. Baseline group characteristics will be summarized in a table with means and standard deviations for continuous data, percentages for categorical data, and medians with interquartile ranges for ordinal data.

Secondary outcomes for this study will include hospital admission rates, emergency department (ED) length of stay (LOS), changes in asthma severity scores, vital sign changes, medication side effects, and total quantity of albuterol given in the ED. Analysis of these variables will be completed using appropriate statistical analysis depending on the nature of the data (t-test for continuous, chi square of Fisher's exact test for categorical, and Mann-Whitney U test for ordinal). Non-parametric tests will be used when appropriate.

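### Does asking the blinded assessor to guess the nebulizer after the response is measured, with no stated analysis, leave the blinding check unusable?

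*Combined protocol and SAP*

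**What the plan says.** Section VI, Research Method, Design, gives one person, P1, the whole sequence of measurements. Before treatment, "As a part of screening, the P1 personnel will perform baseline spirometry measurements prior to consent", and after consent P1 records vital signs and the PAS and PASS scores. A second, unblinded team member opens the assignment and gives the study dose. Then "P1 will perform a post-treatment assessment of the subject including a repeat set of vital signs, pulse-oximetry, asthma scoring, and spirometry measurements". Only after that is the guess taken: "the P1 (blinded) study personnel will be asked to predict which nebulizer was utilized in the study, in order to evaluate adequacy of blinding".

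The Statistical Analysis section covers the primary outcome, the baseline table, the listed secondary outcomes and a conditional regression. For the secondary outcomes it says "Analysis of these variables will be completed using appropriate statistical analysis depending on the nature of the data". The guess is not on that list, and no test, index or threshold is given for it. The protocol does not mention a recorded reason for the guess or a 'don't know' option. It refers to standardized data forms, but these are not part of the document, so whether they carry such items cannot be seen.

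**The concern.** P1 knows both FEV1 values and both sets of scores when guessing. The study hypothesis in Section IV tells P1 which way to lean: "We hypothesize that albuterol delivered with a breath-enhanced nebulizer will lead to statistically greater improvement in" FEV1. An assessor with no knowledge of allocation could therefore pick the breath-enhanced device for good responders and be right more often than chance, provided the hypothesis is true. An above-chance rate could then mean that allocation leaked or that the device worked.

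This matters because P1 is the trial's blinded observer, who coaches effort-dependent spirometry and assigns the asthma scores. The check could raise a false alarm in just the scenario where the trial succeeds. The reason behind a guess, if not recorded at the time, cannot be recovered later.

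**Working it through.** **Inputs from the Sample Size section.** Difference to detect 5 points, power 0.80, alpha 0.05, 64 per arm, 60% with interpretable spirometry. The t-test is two-tailed (Statistical Analysis).

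**The plan's own figures.** 2 × 64 = 128, and 128 / 0.60 = 213.3, in line with "we will need to enroll 213 patients in order to obtain interpretable data on 128 patients". The SD of the FEV1 change is not stated. With SD 10, the standardized difference is d = 5/10 = 0.5, and a two-sample t-test with 64 per arm has power 0.801. SD 10 is therefore a back-solved assumption.

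**Ceiling on correct guesses with no leak.** Suppose every guess is 'breath-enhanced' when the FEV1 change exceeds the midpoint between the arm means. Then

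P(correct) = Φ(d/2) = Φ(0.25) = 0.599.

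This mimics true knowledge in 2 × 0.5987 − 1 = 0.197 of patients, or about 42 of 213. Other SDs give 56.6% (SD 15, d = 0.33) and 63.1% (SD 7.5, d = 0.67).

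**When fewer guesses use response.** If a fraction f follows response and the rest are coin tosses, P(correct) = 0.5 + f × 0.0987. The last two columns give the chance that an exact two-sided binomial test rejects 50%.

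| Scenario, no leak | P(correct) | 128 guesses | 213 guesses |
|---|---|---|---|
| All guesses use response | 0.599 | 58% | 80% |
| Half do | 0.549 | 18% | 27% |
| A quarter do | 0.525 | 7% | 9% |
| All do, true effect 2.5 points | 0.550 | 18% | 27% |
| No device effect | 0.500 | 4% | 4% |

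A misleading result thus needs a real device effect and assessors who lean heavily on response. The 213 column is generous, because it applies the FEV1 effect to every patient although about 128 are expected to have interpretable FEV1. Both columns treat guesses as independent, although the same assessors guess repeatedly.

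**Would recording a reason, and judging blinding on the other guesses, do better?** Take 213 guesses, with half of the uninformed ones driven by response and 0–40% of response-driven guesses given some other reason.

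- *No leak.* False alarms fall from 27% (all guesses tested) to about 4–10%.
- *20% leak, all guesses tested.* P(correct) = 0.2 + 0.8 × 0.549 = 0.639, and the test rejects in 98% of trials.
- *20% leak, non-response guesses only.* Detection, by simulation, is 96–97% if leaked guesses are labelled honestly, about 51–63% if half are labelled as response, and 4–8% if all are.

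The rule gains specificity, but pays for it in sensitivity to the one event the check exists to find. An assessor who saw the device has some incentive to choose the harmless label.

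**The case for a change.** The best case for a change is that it is cheap: two short items with the guess and one extra table, with no effect on treatment, sample size or the primary analysis. Since the guess is collected for one stated purpose, it ought to be able to serve it. Regression of the guess on arm and FEV1 change is only a partial substitute, because assessors may also use scores and vital signs, and because FEV1 is expected to be interpretable in only about 128 of 213 patients.

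Much of this stands. The sequence is as described, no analysis is written down, and an above-chance rate would not by itself show failed blinding. A reason and a 'don't know' option would be useful as descriptive information.

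It does not amount to a fault in the plan. A protocol narrative does not normally list response options, and the form may already hold them. Taking the guess before the assessment is not what this argument asks for; the timing would stay. What is left is an unwritten tabulation for a check that is neither a primary nor a secondary outcome. Arm, guess, FEV1 change and score change are all collected, so the two explanations can be partly separated with what exists. Timing also limits the benefit: this version is dated 30 July 2017, and the Timeline section expected enrolment to run through June 2017, with dates adjustable, so new form items might reach few patients.

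**Conclusion.** No change follows. The blinding check has a real but modest limit of interpretation, which sensible reporting handles: guesses by arm, shown alongside FEV1 change and score change, with an above-chance rate read cautiously if the device also appears to work. A rate near 50% would be broadly reassuring as the plan stands. The FEV1 comparison and the enrolment target are unaffected, and there is a further safeguard on which FEV1 data are used, since a pulmonologist reviews all flow-volume loops and "The pulmonologist involved will be blinded to therapy arm". That safeguard covers loop adequacy, not P1's coaching or scoring.

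The size rests on assumptions outside the document: SD 10 (range 7.5 to 15), a best-case midpoint rule, and independent guesses. Under these, correct guessing without a leak is at most 59.9% (56.6% to 63.1% across that SD range), and 54.9% at SD 10 if half of guesses use response. The labelling and misreporting rates in the last comparison are illustrative too. They are enough to show that judging blinding mainly on non-response guesses is a trade-off and not a clear improvement.

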There is a potential risk to patients of loss of confidentiality. This risk is minimized utilizing the methods described above. If the experimental nebulizer shows decreased efficacy compared to the control arm, subjects may experience less bronchodilation, and subsequently may require more subsequent doses of albuterol, or other adjunctive therapies. There is no reason to believe that patients in the experimental group will experience greater discomfort than those patients in the control group.

Data and safety Monitoring:

This study involves 2 FDA approved nebulizers that have been used clinically for decades. The medication doses are similar to those used by children in the home setting. For these

reasons this study is considered very low risk and equivalent to the ED standard of care for non-study patients. Despite this, a Data and Safety Monitoring Plan will be in place for ongoing evaluation of the safety of this study. The DSMP will consist of the PI ([name]) and the Co-I ([name]) reviewing any reported adverse events within 24 hours of occurrence. Additionally, at the midpoint of the study (subject #107), there will be a scheduled interim analysis. During this analysis we will analyze group difference with regards to adverse event and admission rates. If, during either of these reviews, new information is discovered that would change the risk profile of the study, enrollment will be suspended and the IRB will be notified to help determine a course of action.

IX. Potential Benefits

The potential benefit of this trial is the possibility of a better understanding of the effect of breath-enhanced nebulizer technology on the treatment of acute asthma. Additionally, if we are able to demonstrate significant benefit of this new technology, this may enhance the treatment of future pediatric patients with asthma, at home or in the emergency department. The potential benefit of this study to the individual study patient is largely unknown. Patients who are randomized to the experimental arm of the study may experience greater bronchodilation due to improved medication delivery; however, this benefit is likely minimal given that this study is evaluating only a single dose of albuterol.

X. Sites or Agencies involved in the research project

Research activities will be carried out exclusively at Dell Children's Medical Center.

XI. Review by another IRB

Not applicable.

XII. Citations

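### Does the lack of a rule for admission undermine the comparisons of ED albuterol and ED length of stay?

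*Combined protocol and SAP*

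**What the plan says.** Section VI (Statistical Analysis) lists the secondary outcomes together: hospital admission rates, ED length of stay, changes in asthma severity scores, and then "vital sign changes, medication side effects, and total quantity of albuterol given in the ED". Continuous measures get a t-test, with a non-parametric test where appropriate. The Sample Size text sets an intention-to-treat basis.

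The observation window is set earlier in section VI. After the study dose, data are recorded "regarding subsequent therapy through the remainder of the patients' ED course". For those who go on to a ward, "Patients who are admitted to the hospital will be treated according to the standard of care as determined by the inpatient attending physician". The paragraph ends: "Following disposition from the ED, no further data will be obtained from patients".

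Before randomisation, if consent takes longer than 15 minutes, "a unit dose (2.5mg) of albuterol may be given with a standard t-piece nebulizer up to 3 times as needed". The baseline form covers "nature and duration of current symptoms, and treatments prior to ED arrival".

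No section gives clock times for length of stay, a summary by disposition, or a rule for admitted children. The regression adjustment at the end of section VI covers only the primary endpoint and depends on baseline differences.

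**The concern.** Admission happens after randomisation, may depend on the device, and stops both the albuterol count and the ED clock. A child admitted early could show little albuterol and a short stay while doing badly. The shift could also run the other way, if admitted children receive more ED albuterol or wait longer for a bed.

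Section VIII makes the reading matter. It says that with a less effective device "subjects may experience less bronchodilation, and subsequently may require more subsequent doses of albuterol, or other adjunctive therapies", which invites the inference that a lower total means a better device. If admissions differ between arms, that inference is not secure.

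A second strand is where counting starts. ED doses given before randomisation, up to 3 × 2.5 = 7.5 mg, fall between the two recording windows described, so it is unclear whether they count. At stake is the interpretation of two secondary outcomes.

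**Working it through.** **The plan's own figures.** 128 / 0.60 = 213.3, against 213 stated, so enrolment reproduces. The 64 per arm for a 5-point difference (80% power, two-sided 5%) reproduces only with an SD of about 10 points, which the plan does not state. Neither figure concerns albuterol or length of stay. Every input below is an assumption unless a section is named.

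**Size of the admission component.** Shift = (drop in admission proportion) × (ED amount if discharged minus ED amount if admitted, in children whose admission is averted).

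- Albuterol, 10 fewer admissions per 100: 0.10 × (±5 to ±10 mg) = ±0.5 to ±1.0 mg.
- Length of stay: 0.10 × (±60 to ±120 min) = ±6 to ±12 min.
- With 5 fewer per 100 these halve. With equal admission rates, and no change in who is admitted, the shift is zero.

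**Against what the trial can detect.** With 213 / 2 = 106.5 per arm, the detectable difference is about (1.96 + 0.84) × SD × √(2/106.5). For SD 5 mg this is 2.80 × 5 × 0.137 = 1.92 mg, or 1.93 mg with the t distribution. SD 10 mg gives 3.86 mg; SD 60 and 120 min give 23.1 and 46.3 min. Each shift above is smaller than these.

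**The apparent loss or gain of power.** Take a 1.93 mg reduction at SD 5 mg (80% power) and add the shift:

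| Shift (mg) | −1.0 | −0.5 | +0.5 | +1.0 |
|---|---|---|---|---|
| Power | 99% | 94% | 55% | 27% |

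The arithmetic is right, but it treats 1.93 mg as the truth and the shift as contamination. That presumes another target, such as albuterol use had admission not changed. The plan names the quantity given in the ED. For that quantity the true difference at a +0.5 mg shift is 1.93 − 0.5 = 1.43 mg, and 55% is simply the power to detect 1.43 mg.

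**The apparent false positives.** Simulated t-tests with 106 per arm, a within-disposition SD of 6 mg, no device effect within either disposition group, and admissions of 35% v 25% rejected in about 9% of trials at a 5 mg gap and 16% at a 10 mg gap. With 30% admitted in both arms the rate was about 5%. The excess is not type I error, because mean ED albuterol really does differ, by 0.10 × 5 = 0.5 mg. Check:

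- Total variance = 6² + 5² × (0.35 × 0.65 + 0.25 × 0.75)/2 = 36 + 5.19 = 41.2, so SD = 6.42 mg.
- Standard error = 6.42 × √(2/106) = 0.88 mg.
- 0.5 / 0.88 = 0.57, which gives two-sided power of about 9%.

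The rejection rate is therefore the power to detect a real 0.5 mg difference in ED use.

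**Doses before randomisation.** Suppose a proportion q of children receive 2.5, 5 or 7.5 mg with equal chance. The variance is q × 29.17 − (5q)².

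- q = 0.10: 2.67, SD 1.63 mg.
- q = 0.30: 6.50, SD 2.55 mg.
- q = 0.50: 8.33, SD 2.89 mg.

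These doses precede randomisation, so counting them cannot bias the arm difference. The effect on precision depends on r, the mg of later albuterol that each early mg replaces. The variance with early doses counted is base + (1 − r)² × V; without them it is base + r² × V. The difference is (1 − 2r) × V. Relative to a base of 25 (SD 5 mg), with V from 2.67 to 8.33, counting them changes the variance by +11% to +33% at r = 0, by 0% at r = 0.5, and by −11% to −33% at r = 1. Excluding them helps only if they replace less than half their amount, and the documents do not settle that.

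**The case for a change.** The best case for a change is this. No rule exists, and admissions could plausibly differ: section V cites a paediatric trial of breath-actuated nebulizers, a related device, with fewer admissions, and section VIII plans an interim look at admission rates by arm. Length of stay has neither a start nor a stop, so admitted stays could look short if the clock stops at the decision and long if it stops at departure. Some wording, a table by disposition, a clock starting at randomisation and a ranked sensitivity analysis would cost little.

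Part of this stands. The start and stop times are unwritten, and a lower ED total in an arm with more admissions would not show better bronchodilation.

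The rest does not carry a change. Discharge ends both measures just as admission does, so nothing is censored. The section VIII sentence is a disclosure of risk; no section says that a lower total will be taken as benefit, and the admission rate is reported in the same list. If averted admissions lower ED use, the two results agree and mislead nobody, so only one direction needs care. Section IX expects little individual benefit from a single dose, which makes a 10-point admission difference a generous assumption.

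The remedies also gain little. Ranking admitted children worst imposes an ordering that the plan does not contain and partly repeats the admission outcome. Starting the clock at randomisation changes the named outcome with no shown gain. A new time field may come too late, since section VII.e planned enrolment through June 2017 (though dates could move) and the document is dated 30 July 2017.

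**Conclusion.** No change to the plan is needed. Followed as written, it gives a sound intention-to-treat comparison of two fully observed measures of ED use. What looks like distortion by admission is part of the total effect on those measures. Under the assumed 10-point admission difference it is 0.5 to 1.0 mg or 6 to 12 min, of either sign; the documents supply nothing from which to find its actual size.

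What remains is detail that a competent analyst fills in: apply one start and stop definition to both arms, say whether ED doses before randomisation are counted, and read both outcomes beside the admission rate. Section VII.g lists medical chart copies among the study records, so these choices can be made at analysis. The conclusion rests on taking the outcomes as named, that is, as ED use and not as a proxy for bronchodilation. The primary FEV₁ comparison, measured after the single study dose, and the admission rate are not touched.

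### In children given t-piece albuterol during a consent delay, the primary FEV1 change read literally includes the response to non-randomised doses, and no text moves the baseline

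*Combined protocol and SAP*

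**What the plan says.** The combined protocol and SAP fixes the start of the primary change in section VI, Sample Size: "The primary outcome for this study is change in FEV₁ from initial presentation to reassessment". The screening text in section VI says that "the P1 personnel will perform baseline spirometry measurements prior to consent", and section VII.b repeats that order.

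Between that reading and randomisation, section VI allows treatment. If the consent process causes a delay of more than 15 minutes, "a unit dose (2.5mg) of albuterol may be given with a standard t-piece nebulizer up to 3 times as needed". It adds: "Patients requiring this unit dose of albuterol will still be eligible for enrollment so long as they meet enrollment criteria following this therapy". One entry criterion is an FEV1 limit, since a child above 70% predicted is excluded (Subject Eligibility).

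The assessments placed after consent are vital signs ("Following consent, the P1 personnel will record an initial set of vital signs") and asthma scores ("record baseline asthma scores using multiple previously validated asthma severity scores"). Spirometry is not among them. The post-treatment list does name it: "a repeat set of vital signs, pulse-oximetry, asthma scoring, and spirometry measurements". The randomised treatment is stated as: "P2 will administer a single 5mg dose of albuterol via the appropriate nebulizer as determined by randomization".

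The primary test is an unadjusted two-tailed t-test or its non-parametric equivalent. Regression is planned only if the groups differ significantly at baseline (section VI, Statistical Analysis). The baseline form covers treatment before arrival at the ED, and a later form covers therapy after the experimental stage. Total ED albuterol is a secondary outcome.

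**The concern.** The trial asks which device gives the larger response to one 5 mg dose. For a child treated during a consent delay, a change measured from the pre-consent FEV1 answers a different question: the response to the delay doses plus the study dose. All delay doses go through the standard t-piece, whichever arm the child later joins.

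Three things could follow. The primary outcome could carry variance unrelated to the randomised treatment, including chance imbalance between arms in the share pre-treated. The mean change reported within each arm could exceed the response to the study dose. And if a repeat FEV1 is taken for the eligibility re-check, two analysts could use different baselines for the same child, because the plan does not say which value to use. If it is not taken, it cannot be recovered later.

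The plan's conditional regression need not deal with this. Pre-randomisation albuterol is not named as a covariate, and adjustment depends on a significance check at baseline.

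**Working it through.** **1. The plan's own figure.** Inputs from Sample Size and Statistical Analysis: difference 5 points, power 0.80, two-sided alpha 0.05, 64 per arm. No SD is given. For a two-sample t-test, 64 per arm gives 80% power at an SD of 10.02, and power at SD 10 is 0.801. SD 10 is therefore a back-calculated assumption. The stated 64 per arm is not in dispute.

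**2. Dose arithmetic.** Delay doses: 1 to 3 × 2.5 mg = 2.5 to 7.5 mg. Relative to the study dose: 2.5/5 = 0.5 and 7.5/5 = 1.5.

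**3. Sequence in section VI.** Baseline spirometry; consent process, with delay doses if needed; vital signs and asthma scores; randomisation; 5 mg study dose; reassessment at 15 minutes. The literal FEV1 change spans the delay doses. In that order, the changes in vital signs and asthma scores start after them.

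**4. Size, illustration only.** Assumptions, none of them in the documents: share pre-treated p; gain from the delay doses with mean g and SD s; correlation r between that gain and the study-dose response; study-dose response SD 10; true difference kept at 5.

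Variance of the literal change = 100 + p(1−p)g² + p·s² + 2·p·r·s·10.

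Example, p = 0.10, g = s = 5, r = 0: 100 + 0.09 × 25 + 0.10 × 25 = 104.75, so SD = 10.23 and power = 0.783 at 64 per arm.

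| p | g, s | r | Variance | Power |
|---|---|---|---|---|
| 0.10 | 5, 5 | 0 | 104.75 | 0.783 |
| 0.30 | 5, 5 | 0 | 112.75 | 0.753 |
| 0.10 | 10, 10 | 0 | 119 | 0.730 |
| 0.30 | 10, 10 | 0 | 151 | 0.627 |
| 0.10 | 5, 5 | −0.5 | 99.75 | 0.802 |
| 0.30 | 5, 5 | −0.5 | 97.75 | 0.810 |

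The last two rows show no loss. If children who gain more from the delay doses have less left to gain from the study dose, the extra variance can vanish. The break-even correlation is r = −[(1−p)g² + s²]/(20s). For g = s = 5 it is −0.475 (p = 0.10) and −0.425 (p = 0.30); for g = s = 10 it is −0.95 and −0.85.

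**5. With the 70% re-check applied.** The table keeps every pre-treated child, although those above 70% after the doses would be excluded. A simulation drew baseline FEV1 with mean 55 (the plan's figure) and assumed SD 8, 10 or 12, cut at 70, added a gain with g of 5 or 10 and s of 0, 5 or 10, and kept totals up to 70 (3,000,000 draws per case). Power ranges:

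- r = 0: 0.759–0.793 (p = 0.10) and 0.689–0.781 (p = 0.30).
- r = −0.5, with gain SD above 0: 0.776–0.802 and 0.750–0.810.

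These ranges presume that the re-check FEV1 was taken but not used as baseline.

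**6. Within-arm change.** Amount added = p × mean gain among children kept. In the filtered cases this is 0.22–1.00 points at p = 0.10 and 0.65–3.00 at p = 0.30, against the 10-point improvement that the plan expects with standard care.

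**The case against.** **A baseline is named.** A reader might infer that the baseline is simply undefined. The literal text does not support that: section VI and section VII.b both call the pre-consent reading baseline, and the outcome starts at initial presentation. What stands is narrower. Under the literal reading the outcome includes non-randomised treatment. Under the reading that the eligibility re-check supplies a new FEV1, that problem goes, but the plan never says that the new value takes over.

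**Randomisation protects the comparison.** Because the delay doses use the control type of device, a reader might infer bias between arms. The documents do not support that either. The doses come before concealed assignment and are equally likely in both arms, so any imbalance is due to chance, and the t-test keeps its type I error.

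**The power figures are assumed.** This stands. The provision applies only when consent causes a delay of more than 15 minutes and a dose is needed. Nothing supports a 30% share. At shares of 2% and 5%, with g = s = 5 and independence, the formula gives power of 0.798 and 0.792. The lowest filtered value, 0.689, combines the largest share with a mean gain equal to the plan's whole expected improvement.

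**Supporting details are soft.** The different starting points for FEV1 and for the scores rest on sentence order. A PAS of 0 is an exclusion, so a pre-dose score may exist. Delay doses could be derived by subtracting the 5 mg study dose and later therapy from total ED albuterol, if those records are complete. I therefore give both points little weight.

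**Conclusion.** The concern holds in a limited form. As written, the primary change can include the response to 2.5–7.5 mg of non-randomised albuterol, and no text makes the re-check FEV1 the baseline. This affects the clarity of the outcome, possibly its variance, and the size of the within-arm change. It does not affect the validity of the between-arm test.

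The size is unknown. A reader might take the power ranges as evidence of an underpowered trial. They are not: they rest on an assumed share, gain, gain SD and correlation, and on an SD of 10 inferred from the sample size. Some plausible settings show no loss. The case for change rests on the definition of the outcome and on the low cost of settling it in advance. It should be fixed; confidence is medium.

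**What to change.** 1. Define the primary change as running from the last acceptable FEV1 before randomisation to the 15-minute reassessment. In pre-treated children this is the eligibility re-check value, where one exists.
2. Make the primary analysis a linear model of FEV1 change on treatment arm, with baseline FEV1 and pre-randomisation ED albuterol (number of doses, or yes/no) as pre-specified covariates. This replaces regression triggered only by significant baseline differences.
3. Record pre-randomisation ED doses (0 to 3) as a separate item, so that the covariate does not depend on back-calculation from total ED albuterol.

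In the filtered illustration, the re-set baseline gives power of 0.801–0.808, if the study-dose response has SD 10 in pre-treated children too. A yes/no covariate alone gives 0.771–0.801 (p = 0.10) and 0.714–0.801 (p = 0.30) under independence, and 0.801–0.811 and 0.801–0.831 at correlation −0.5. The re-set baseline may therefore add no power when the correlation is negative; its gain is then a clearly defined outcome. Adjustment for baseline FEV1 was not modelled. Neither step removes a true weakening of the device effect in pre-treated children.

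The cost is wording in two places, one data item and a little more analysis work. If the re-check is not already done by spirometry, a new session of 3 to 8 manoeuvres should not be required for this purpose: the plan itself warns of fatigue and expects about 60% interpretable spirometry. In that case the pre-consent reading stays as baseline and the covariates alone apply. No change to the dosing provision is proposed.
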